Laboratory space: Laboratory space in Williams Hall contains filtration devices to remove any secondhand smoke or aerosol (from cigarettes or ENDS). In consultation with [name] at Virginia Commonwealth University and [name], Executive Director of Facilities at EVMS, approximately \$50,000 was spent designing and equipping these rooms. This laboratory was designed for smoking research and includes a ventilation system so that others are not exposed to second-hand smoke unduly.

Sample size: A total of 30 participants are planned to allow for statistical power to examine differences (Within-Subjects) in the physiological and subjective effects of the products. Using a Repeated Measures Within-Subjects design, this will allow for detection of a large effect size (Cohen, 1992; Faul et al., 2009). We may consent up to 75 participants in order to obtain 30 participants who complete the entire study.

Recruitment: We will recruit current cigarette smokers using a recruitment database submitted separately (PR-2871-EVMS). Potential participants will find this recruitment database via advertising on Craigslist, newspapers, internet forums, flyers in the local area, and local clinics. There is a flyer specifically for this study that will direct individuals to participate in the registry online questionnaire. Screening data will be obtained from this online questionnaire. See separate protocol submitted. Screening data will be compared against the inclusion and exclusion criteria listed below to determine if participant is eligible for this study. Eligible participants will be contacted to provide more information about the study. Participants will be told they can smoke as normal for their first visit, but must abstain for 12 hours (typically overnight) before the 3 other visits. Those who meet screening criteria and are still interested in the study will be scheduled to come in for laboratory visits.

Inclusion Criteria: All participants must be healthy (determined by self-report), between the ages of 18-55, willing to provide informed consent, and willing to attend the EVMS lab 4 times and abstain from smoking for 12 hours (typically overnight) for 3 of these visits. Participants must smoke at least 10 cigarettes per day (i.e., be regular cigarette smokers). Self-report of smoking will be bioverified on the initial screening visit.

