used for each dependent variable. There are three within-subject tobacco products (own-brand cigarette, ENDS with unprotonated nicotine, ENDS with protonated nicotine) and four within-subject time points (pre-use, post-directed 10 puff session, pre-*ad lib* use session, post-*ad lib*). Three (condition) x four (time) repeated measures ANOVAs will assess plasma nicotine and heart rate (HR). Questionnaire items (or craving factors) will be examined individually using separate ANOVAs. Analyses conducted on the Hughes-Hatsuhashi Withdrawal scale, the Tiffany Drobis Questionnaire of Smoking Urges, and the Direct Effects of Nicotine (DEN) have 4 levels of time. The Direct Effects of E-cigarettes scale, unlike the DEN, only assesses reactions to the tobacco product and thus will have only 2 levels of time. Videorecordings will be evaluated via established methodology (Blank et al., 2009).

Any violations of sphericity will be adjusted using Huynh-Feldt corrections. In order to maintain statistical power and limit type 1 error for plasma nicotine, HR, and subjective effects, planned contrasts (paired samples *t*-tests) will be conducted across conditions at the two time points immediately after each use bout (e.g., each post-use session). At these two post-use timepoints, the mean value for each outcome measure in the protonated nicotine condition will be compared to the corresponding mean values in the unprotonated nicotine and cigarette conditions. Because these comparisons are non-orthogonal, a Bonferroni correction will be applied (Keppel, 1991).

References

CDC, 2011. Quitting smoking among adults--United States, 2001-2010. *MMWR Morb Mortal Wkly Rep* 60, 1513-1519.

Cohen, J., 1992. A power primer. *Psychological bulletin* 112, 155.

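### Holm's step-down procedure would serve the planned contrasts better than plain Bonferroni: an inexpensive gain in power, not the correction of an error

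*Combined protocol and SAP*

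**What the plan says.** The Data Analysis section specifies "planned contrasts (paired samples *t*-tests"), to be carried out "at the two time points immediately after each use bout". At each of these, "the mean value for each outcome measure in the protonated nicotine condition will be compared to the corresponding mean values in the unprotonated nicotine" condition; the same comparison is made with own-brand cigarette. That makes two contrasts per time point and four per outcome. The section introduces the contrasts as a way to preserve power and to "limit type 1 error for plasma nicotine, HR, and subjective effects", and then says: "Because these comparisons are non-orthogonal, a Bonferroni correction will be applied (Keppel, 1991").

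No step-down or other sequential version is named. The section gives no family-wise alpha, no divisor (two or four), no ranking of the two contrasts and no simultaneous confidence intervals. On the number of outcomes it says: "Questionnaire items (or craving factors) will be examined individually using separate ANOVAs". The Sample size section says: "A total of 30 participants are planned to allow for statistical power to examine differences", and describes the detectable effect only as large.

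**The concern.** Single-step Bonferroni holds every test at the smallest threshold, even after other hypotheses in the family have been rejected. Holm tests the smallest p-value at that same threshold and relaxes it for each later one. It controls the family-wise error under any dependence, so the non-orthogonality that the plan gives as its reason for correcting is no reason to prefer Bonferroni to Holm.

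Salt versus regular is the contrast that isolates protonation, because the device, nominal strength and flavor matching are the same in both ENDS conditions (Product consumption). If salt versus cigarette is clearly different and is rejected, single-step Bonferroni leaves that test's share of alpha unused. Power for salt versus regular at moderate effect sizes is then lower than it needs to be.

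**Working it through.** **Inputs from the plan.** n = 30 completers; paired t-tests; two contrasts at each of two time points.

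**Assumptions, because the plan is silent.** Family-wise alpha 0.05, two-sided. Family of two (per time point) or four (both time points). Correlation 0.5 between the two contrasts: if the three conditions have equal variance σ² and equal correlation ρ, two differences that share the salt mean have covariance σ²(1 − ρ) and variance 2σ²(1 − ρ) each, hence correlation 0.5. Correlation 0.5 between time points. Effects are standardised paired differences, dz.

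**1. The plan's own figure.** The sample size cannot be reproduced uniquely, since alpha, power and a numerical effect are missing. Taking large as dz = 0.8, the power of one paired t-test comes from the noncentral t distribution with 29 degrees of freedom and noncentrality dz·√30 = 0.8 × 5.477 = 4.38. It is 98.8% at 0.05, 97.4% at 0.025 and 95.0% at 0.0125. So n = 30 is consistent with its claim, with Bonferroni included.

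**2. Thresholds.**
- Family of two: Bonferroni uses 0.025 and 0.025; Holm uses 0.025, then 0.05.
- Family of four: Bonferroni uses 0.0125 throughout; Holm uses 0.0125, 0.0167, 0.025, 0.05.

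No Holm threshold is below Bonferroni's, so every Bonferroni rejection is kept.

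**3. Ceiling on the gain, family of two.** Holm changes the salt-versus-regular result only when its p lies between 0.025 and 0.05 and salt versus cigarette has p ≤ 0.025. The gain therefore cannot exceed power at 0.05 minus power at 0.025:
- dz 0.4: 56.3 − 44.2 = 12.1 points
- dz 0.5: 75.4 − 64.7 = 10.7 points
- dz 0.6: 88.8 − 81.6 = 7.2 points
- dz 0.8: 98.8 − 97.4 = 1.4 points

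**4. Simulated power per salt-versus-regular contrast** (40,000 simulated trials per scenario, Bonferroni → Holm):

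| Salt vs cigarette, absolute dz | Salt vs regular dz | Family of two | Family of four |
|---|---|---|---|
| 0.8 | 0.4 | 44% → 56% | 34% → 49% |
| 0.8 | 0.5 | 65% → 75% | 54% → 70% |
| 0.8 | 0.6 | 82% → 89% | 73% → 86% |
| 0.8 | 0.8 | 97% → 99% | 95% → 99% |
| 0 | 0.4 | 44.1% → 44.3% | 33.5% → 35.3% |
| 0 | 0.5 | 65.0% → 65.1% | 53.4% → 55.8% |
| 0 | 0.6 | 81.7% → 81.9% | 72.8% → 75.3% |
| 0 | 0.8 | 97.5% → 97.5% | 95.1% → 96.1% |

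Between these extremes, with both contrasts at an absolute dz of 0.5, power goes from 64% to 72% (family of two). With all four at dz = 0.5 it goes from 54% to 64%. The sign of the cigarette effect made almost no difference.

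**5. Family-wise error** (100,000 simulated trials per scenario, Bonferroni / Holm):
- All nulls true: 4.7% / 4.7% (family of two); 4.6% / 4.6% (family of four).
- Only the cigarette contrasts real, absolute dz 0.8: 2.5% / 4.8% (two); 2.5% / 4.5% (four).
- Only the cigarette contrasts real, absolute dz 1.2: 2.5% / 4.9% (two); 2.4% / 4.8% (four).

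**The case against.** Bonferroni is a valid method and the plan gives a reason for correcting. A reader might infer that the multiplicity handling is wrong; the documents do not support that, since the error rate is controlled within whatever family is meant.

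A reader might also infer that the plan sacrifices the one comparison the trial was set up to make. The research questions name regular nicotine and own-brand cigarette together and rank neither. If salt versus regular did have priority, ordering the contrasts would be a more direct remedy than Holm, whose benefit there depends on rejecting something else first.

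The largest gains need a strong salt-versus-cigarette difference. The documents give no effect size for either contrast, and salt may resemble the cigarette on some items. With a cigarette effect of dz = 0.2 to 0.3 and salt versus regular at 0.5, the gain is only about 0.5 to 2 points (family of two) or 3 to 4 points (family of four). Nor can the family of four be taken for granted: the non-orthogonality argument fits the two contrasts within a time point at least as well.

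Finally, Holm is not free of consequence. When only the cigarette contrasts are real, the chance of a false salt-versus-regular finding roughly doubles, from about 2.5% to about 5%. This is within the nominal level, but Bonferroni's extra caution has some value when many items are tested separately and no correction across them is stated.

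All of this stands as a limit on size and tone. None of it removes the point that Holm, on the same family, keeps every Bonferroni rejection under the same guarantee.

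**Conclusion.** The point holds as an inexpensive improvement. Holm's dominance over Bonferroni on the same family is a mathematical result and needs none of the assumed effects. The size of the benefit does depend on them. With a strong salt-versus-cigarette effect (dz = 0.8) and a moderate salt-versus-regular effect (dz = 0.4 to 0.6), it is about 7 to 12 points for a family of two and about 13 to 16 points for a family of four. At the large effect for which the trial was sized, or if salt and cigarette do not differ, it is small. The single-step reading is itself an inference from the absence of any step-down wording. Neither method controls error across the separately tested outcomes, so the change does not settle that question.

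**What to change.** Before data are analysed, replace the Bonferroni clause in the Data Analysis section with wording such as: *the Holm step-down Bonferroni procedure will be applied to the planned contrasts within each outcome, with the family defined as [two contrasts per time point / four contrasts across both time points] and a two-sided family-wise alpha of [value]; Holm-adjusted p-values will be reported.* The sponsor should choose one option for each bracket. The family and alpha have to be stated whichever method is kept, since neither can be carried out without them.

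The cost is one sentence, with no added participants, visits or data. The drawback is that simultaneous confidence intervals matching Holm are less simple than Bonferroni intervals; the plan does not call for any.
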